4.5.2.1. Adverse Events of Special Interest

Active TB, malignancy and possible Hy'sLaw cases are defined as AESI. The listing for each AESI will be provided.

4.5.3. Additional Safety Assessments

4.5.3.1. Clinical Laboratory Tests

Descriptive statistics will be presented for selected chemistry, hematology laboratory tests at scheduled time points.

Change/percent change from baseline will be summarized for chemistry, hematology tests and displayed. A box plot of laboratory measurements and change from baseline will be provided.

Applicable laboratory results will be graded according to NCI-CTCAE version 5.0.

Shift summaries from baseline laboratory value to the worst NCI-CTCAE, version 5.0 grade in chemistry and hematology tests with NCI-CTCAE, version 5.0 will be presented.

All laboratory parameters and the participants with toxicity grade ≥ 2 will be listed.

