- j. For W16 and W52: Height will be measured only for participants  $< 18$  years on the first date of Screening.
- k. Vital signs will include temperature, pulse/heart rate, respiratory rate, and blood pressure.
- l. A 12-lead ECG will be performed locally. Participants should rest in a supine position for at least 5 minutes before ECG recording and should refrain from talking or moving arms or legs.
- m. PHQ-9 and C-SSRS will be completed after PROs and before all other study procedures.
- n. If TB is suspected at any time during the study, a chest radiograph or chest CT, and QuantiFERON-TB® or T-SPOT® test should be performed.
- o. A negative urine test result is required at each visit prior to dispensing study intervention. A urine pregnancy test may be performed at any time during the visit, including before PRO collection.
- p. At Week 0, all blood samples should be collected prior to study intervention administration, and the date and time of collection should be recorded as instructed in the Laboratory Manual. At all other study visits where applicable, the date and time of the dose prior to the PK sample should be recorded as instructed in the CRF completion guidelines.
- q. Fasting requirement for lipid panel:  $\geq 6$  h unless medically contraindicated.

- r. Urinalysis may be performed any time during the study visit including before PRO collection.
- s. Collect 1 trough and 1 peak sample at Week 4 and Week 16. Details to be specified during training. If peak/trough collection at the Week 4 and Week 16 visits is not feasible, collection at an alternative visit is allowed.
- t. All medications taken and new or worsening AEs reported after signing the ICF will be recorded. See CRF completion guidelines.

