### 5.3. Lifestyle Considerations

Participants must be willing and able to adhere to the following lifestyle restrictions to be eligible for participation:

1. Recommended to be up to date on all age-appropriate vaccinations prior to screening per routine medical guidelines. It is strongly recommended that participants will have completed a locally approved (or emergency use-authorized) COVID-19 vaccination regimen at least 2 weeks prior to study-related visits or procedures. Study participants should follow applicable local vaccine labeling, guidelines, and standards-of-care for participants receiving immune-targeted therapy when determining an appropriate interval between vaccination and study enrollment (Section 6.9.1.3).
2. Refer to Section 6.9 for details regarding prohibited and restricted therapy during the study.
3. Agree to take study interventions and comply with fasting requirements (Section 6.1).
4. Agree to fast for at least 6 hours prior to lipid panel blood sample collection unless medically contraindicated (Section 1.3).
5. Strenuous exercise (eg, body building, long distance training [running/cycling]) may affect study specified assessments and safety laboratory results; for this reason, strenuous exercise should be avoided within 2 to 3 days before all planned study visits where laboratory tests are collected.
6. Agree to use sun protective measures (such as a hat, sunglasses, protective clothing, sunscreen), limit prolonged exposure to natural sunlight, and avoid artificial sunlight (tanning beds or phototherapy) during study participation.
7. For adolescent participants, who are not of legal age of consent, a legal guardian or primary caregiver is recommended to:
  - a. Accompany the participant to the study site on each assessment day according to the Section 1.3.
  - b. Accurately and reliably dispense study intervention as directed.

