#### Protocol-Required Laboratory Assessments

Laboratory Assessments	Parameters		
Hematology	Platelet count Red blood cell (RBC) count Hemoglobin Hematocrit	RBC Indices: Mean Corpuscular Volume (MCV) Mean Corpuscular Hemoglobin (MCH) % Reticulocytes	White blood cell (WBC) count with Differential: Neutrophils Lymphocytes Monocytes Eosinophils Basophils
	Note: A WBC evaluation may include any abnormal cells, which will then be reported by the laboratory. An RBC evaluation may include abnormalities in the RBC count, RBC parameters, or RBC morphology, which will then be reported by the laboratory. In addition, any other abnormal cells in a blood smear will also be reported.		
Clinical Chemistry	Sodium Potassium Chloride Bicarbonate Blood urea nitrogen Creatinine Glucose (non-fasting) Aspartate aminotransferase (AST)/Serum glutamic-oxaloacetic Alanine aminotransferase (ALT)/Serum glutamic-oxaloacetic Gamma-glutamyltransferase estimated glomerular filtration rate (eGFR) high-sensitivity C reactive protein (hsCRP)	Total bilirubin (Tbili) and Direct bilirubin Alkaline phosphatase Creatine phosphokinase (CPK) Lactic acid dehydrogenase (LDH) Uric acid Calcium Phosphate Albumin Total protein Cholesterol Triglycerides Magnesium	
	Details of liver chemistry stopping criteria and required actions and follow-up are given in Appendix 5: Liver Safety: Suggested Actions and Follow-up Assessments . Possible Hy's Law case (ALT or AST $\geq 3 \times$ ULN and Tbili $\geq 2 \times$ ULN) reporting requirements are defined in Section 8.4.1.		
Lipid Panel	Total cholesterol High-density lipoprotein (HDL) Low-density lipoprotein (LDL; calculated) Triglycerides		
	Note: Fasting requirements are described in the SoA (Section 1.3).		

Laboratory Assessments	Parameters	
Routine Urinalysis	Dipstick Specific gravity pH Glucose Protein Blood Ketones Bilirubin Urobilinogen Nitrite Leukocyte esterase	Sediment (if dipstick result is abnormal) RBC WBC Epithelial cells Crystals Casts Bacteria
	If dipstick result is abnormal, microscopy will be used to measure sediment.  In the microscopic examination, observations other than the presence of WBC, RBC and casts may also be reported by the laboratory.	

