4.1.2. Baseline

The baseline measurement for efficacy endpoints is defined as the closest measurement taken prior to or on the first study agent administration date. The baseline measurement for other endpoints including safety, PK and immunogenicity is defined as the closest measurement taken prior to the time of the first study agent administration.

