Hypernatremia	Sodium >ULN – 150 mmol/L	Sodium >150 – 155 mmol/L; intervention initiated	Sodium >155 – 160 mmol/L; hospitalization indicated	Sodium >160 mmol/L; life-threatening consequences	Clinical signs and symptoms are not taken into consideration for grading.

CTCAE Term	Grade 1	Grade 2	Grade 3	Grade 4	Janssen Implementation Notes
Hypertriglyceridemia	Triglycerides 150 mg/dL - 300 mg/dL; 1.71 mmol/L - 3.42 mmol/L	Triglycerides >300 mg/dL - 500 mg/dL; >3.42 mmol/L - 5.7 mmol/L	Triglycerides >500 mg/dL - 1000 mg/dL; >5.7 mmol/L - 11.4 mmol/L	Triglycerides >1000 mg/dL; >11.4 mmol/L; life-threatening consequences	Clinical signs and symptoms are not taken into consideration for grading.
Hypoalbuminemia	Albumin <LLN - 3 g/dL; <LLN - 30 g/L	Albumin <3 - 2 g/dL; <30 - 20 g/L	Albumin <2 g/dL; <20 g/L	Life-threatening consequences; urgent intervention indicated	Clinical signs and symptoms are not taken into consideration for grading.
Hypocalcemia	Corrected serum calcium of <LLN - 8.0 mg/dL; <LLN - 2.0 mmol/L; Ionized calcium <LLN - 1.0 mmol/L	Corrected serum calcium of <8.0 - 7.0 mg/dL; <2.0 - 1.75 mmol/L; Ionized calcium <1.0 - 0.9 mmol/L; symptomatic	Corrected serum calcium of <7.0 - 6.0 mg/dL; <1.75 - 1.5 mmol/L; Ionized calcium <0.9 - 0.8 mmol/L; hospitalization indicated	Corrected serum calcium of <6.0 mg/dL; <1.5 mmol/L; Ionized calcium <0.8 mmol/L; life-threatening consequences	Clinical signs and symptoms are not taken into consideration for grading. Note: For Hypercalcemia or Hypocalcemia in the CTCAE Lab Toxicity grading scale, the reference ranges from serum calcium (ULN /LLN) from the local or central lab are being utilized.
Hypoglycemia	Glucose <LLN - 55 mg/dL; <LLN - 3.0 mmol/L	Glucose <55 - 40 mg/dL; <3.0 - 2.2 mmol/L	Glucose <40 - 30 mg/dL; <2.2 - 1.7 mmol/L	Glucose <30 mg/dL; <1.7 mmol/L; life-threatening consequences; seizures	Clinical signs and symptoms are not taken into consideration for grading. Urine glucose is not graded.
Hypokalemia	Potassium <LLN - 3.0 mmol/L	Symptomatic with Potassium <LLN - 3.0 mmol/L; intervention indicated	Potassium <3.0 - 2.5 mmol/L; hospitalization indicated	Potassium <2.5 mmol/L; life-threatening consequences	“Symptomatic” ranges are applied for grade 2, grade 1 not assigned, ie, worst case applied. Clinical signs and symptoms are not taken into consideration for grading of grade 3 and 4.

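### The lipid shift table sets a normally fasting Week 0 baseline against values mostly drawn with no fasting requirement, so it can overstate triglyceride worsening

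*SAP*

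**What the plan says.** **Two panels, one fasting rule.** Protocol Appendix 1 lists cholesterol and triglycerides in the lipid panel and again under clinical chemistry, where the entries run "Albumin Total protein Cholesterol Triglycerides Magnesium". The glucose in that chemistry panel is labelled non-fasting. The fast attaches to the lipid panel only: the Schedule of Activities has a footnote headed "Fasting requirement for lipid panel" (6 hours or more, with a medical exception), and Protocol section 5.3 asks participants to "Agree to fast for at least 6 hours prior to lipid panel blood sample collection unless medically contraindicated".

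**Schedule.** The lipid panel is drawn at Weeks 0, 16 and 52 and has no row in the long-term extension (LTE) schedule. Chemistry is drawn at Week 0, at most later visits to Week 52, and at five scheduled LTE visits.

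**Baseline.** For safety data, SAP section 4.1.2 takes the "closest measurement taken prior to the time of the first study agent administration".

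**Analysis.** SAP section 4.5.3.1 summarises change from baseline for chemistry tests, tabulates "Shift summaries from baseline laboratory value to the worst NCI-CTCAE, version 5.0 grade in chemistry and hematology tests", and lists participants with Grade 2 or higher. SAP Appendix 7 starts Grade 1 hypertriglyceridemia at "Triglycerides 150 mg/dL - 300 mg/dL", with further cuts above 300, 500 and 1000 mg/dL. It grades high cholesterol from above the upper limit of normal. Neither section mentions fasting, and neither says which result counts when both panels are drawn at one visit.

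**The concern.** By attaching a fast to the lipid panel, the protocol treats fasting as a condition for reading lipids. The SAP then compares a baseline collected under that condition with follow-up values mostly collected without it. The comparison uses the worst grade, so the highest reading decides each participant's result.

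The study has one arm, so no control group would show the same artefact and allow it to be subtracted. With 8 participants per disease group, one reclassified participant is 1/8 = 12.5%. SAP section 4.8 also drops the protocol's summaries of abnormal and markedly abnormal laboratory results, on the ground that the laboratory tables and listings carry the information. The affected outputs are therefore the ones a reader must use.

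**Working it through.** The plan states no figure on this point, so there is none to reproduce. The check has three parts.

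**1. Count of draws (both Schedules of Activities)**

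- Chemistry after baseline to Week 52: Weeks 4, 8, 12, 16, 20, 24, 28, 32, 36, 44, 52 = 11.
- Chemistry in the LTE: Weeks 64, 88, 112, 136, 156 = 5. Early-termination and conditional follow-up draws are not counted.
- Lipid panel after baseline: Weeks 16 and 52 = 2. The table's columns are broken in the text available; Week 52 is inferred for the last mark.

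| Through | Chemistry draws | At a fasting lipid-panel visit | No fasting requirement |
|---|---|---|---|
| Week 24 | 6 | 1 | 5/6 = 83% |
| Week 52 | 11 | 2 | 9/11 = 82% |
| Week 156 | 16 | 2 | 14/16 = 88% |

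If the lipid-panel results at Weeks 16 and 52 are counted as separate values, the shares are 5/7 = 71%, 9/13 = 69% and 14/18 = 78%. Most later values lack a fasting rule on either count.

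**2. Distance to a grade boundary (SAP Appendix 7 cuts; starting values chosen for illustration)**

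- From 140 mg/dL (Grade 0) to the Grade 1 boundary: 150/140 = 1.07, a rise of about 7%.
- From 260 mg/dL (Grade 1) to the Grade 2 boundary: 300/260 = 1.15, a rise of about 15%. Above that boundary the participant also enters the Grade 2 or higher listing.

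Both starting values lie near a cut. The documents do not say how many participants would.

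**3. Meals versus worst-of-many selection (illustrative simulation)**

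Every parameter here is an assumption: median triglycerides 100 or 130 mg/dL, between-person log SD 0.45, within-person CV 10% to 30%, no drug effect, and the meal effect applied at every draw without a fasting requirement. The entries are the share of participants shifting to a worse triglyceride grade, as ranges over the medians and CVs.

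| Through | No meal effect | 10% | 20% | 30% | Fasting visits only |
|---|---|---|---|---|---|
| Week 24 | 10–42% | 17–50% | 25–58% | 34–66% | 4–16% |
| Week 156 | 13–57% | 22–66% | 31–74% | 40–80% | 6–24% |

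A meal effect adds to the shifts. The first column shows that taking the worst of 6 to 16 values against one baseline produces many shifts with no meal effect at all. The last column is lower than the first only because it uses one or two values, so that gap is not evidence about meals.

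**The case against.** The strongest reply is that no fasting requirement is not the same as a fed sample. Nothing in the documents says participants eat before chemistry draws. The drug is taken on waking with an empty stomach, and at Week 4 it is taken on site with a pre-dose sample. This stands against any claim that the table will show worsening caused by meals. It does not remove the mismatch. The dosing rule bars food for only 2 hours before and 30 minutes after the dose, and at most visits a participant can dose at home, eat and attend in full compliance. Setting Week 4 aside still leaves 8 of 11 draws to Week 52 and all 5 in the LTE.

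Other points that stand:

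- Weeks 16 and 52 are fasting visits, so change from Week 0 is like for like there. By-visit tables and full listings in about 16 participants let a careful reader compare those visits with the rest.
- The medical exception means that even the Week 0 fast is not guaranteed.
- The descriptive statistics cover a selection of tests that is not named. Appendix 7 looks like a general scale, since it also grades tests absent from Protocol Appendix 1, such as lipase and haptoglobin. Lipids might be left out of some outputs, but nothing excludes them from grading or the shift table.
- Lipids are neither a named endpoint nor an adverse event of special interest, and no formal testing is planned.

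A reader might also infer that values without a fasting requirement should be dropped from grading. That would remove 14 of 16 scheduled chemistry draws, including every LTE value and any Grade 3 or 4 triglyceride outside Weeks 16 and 52. The mismatch does not justify that loss of safety data.

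**Conclusion.** The mismatch is in the documents: a normally fasting baseline, 9 of 11 later chemistry draws to Week 52 and 14 of 16 to Week 156 without a fasting requirement, worst-grade selection, and no control arm. The lipid shift table, the Grade 2 or higher listing and mean change at visits other than Weeks 16 and 52 can overstate triglyceride worsening.

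The size is unknown. The documents give no meal effect and no lipid distribution, so the 7% and 15% crossing points and the simulated ranges are illustrations. Part of any shift would come from taking the worst of many values. A reader might infer that cholesterol is affected equally; the documents do not show this, and any effect there is an assumption. The count rests on reading the last lipid-panel mark as Week 52; another late visit would not change the conclusion.

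This is a cheap improvement to a safety table. It does not touch the primary endpoints.

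**What to change.** In SAP section 4.5.3.1 and Appendix 7:

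- Present change from baseline and CTCAE shift for triglycerides and cholesterol at the fasting lipid-panel visits (Weeks 0, 16 and 52), and name this as the row used to interpret a drug effect.
- Show it next to the all-samples worst-grade row, with every value still graded.
- Flag each lipid value in tables and listings by whether a fast was required at that draw.
- State which result is used when both panels are drawn at one visit.

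The cost is SAP wording, one programming filter and one extra table row; no new sample is needed. The fasting row will be thin: only Week 16 after baseline at the Week 24 lock, and nothing from the LTE.

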4.5.3.2. Vital Signs

Continuous vital sign parameters including temperature, respiratory rate, weight, pulse and blood pressure (systolic and diastolic) will be summarized at each assessment time point. Change from baseline will be also summarized. Descriptive statistics (mean, standard deviation, median, minimum and maximum) will be presented.

Incidence of markedly abnormal vital signs during intervention, as defined in [Table 2](#), will be summarized for participants who had at least 1 postbaseline assessment for that vital sign. A listing of participants with treatment-emergent markedly abnormal vital signs will be presented, along with a listing of all vital sign measurements.

Incidence of treatment-emergent abnormal vital signs during intervention, as defined in [Table 2](#), will be summarized for participants who had a baseline assessment and at least 1 postbaseline assessment for that vital sign.

Table 2: Markedly Abnormal Vital Signs

Vital Sign	Criteria
Pulse	>120 bpm and with >30 bpm increase from baseline
	<50 bpm and with >20 bpm decrease from baseline
Systolic blood pressure	>180 mm Hg and with >40 mm Hg increase from baseline
	<90 mm Hg and with >30 mm Hg decrease from baseline
Diastolic blood pressure	>105 mm Hg and with >30 mm Hg increase from baseline
	<50 mm Hg and with >20 mm Hg decrease from baseline
Temperature	>38°C and with $\geq 1^{\circ}\text{C}$ increase from baseline
Respiratory rate	>20 breaths per minute

4.5.3.3. Columbia-Suicide Severity Rating Scale (C-SSRS)

The C-SSRS will be used as a screening tool to prospectively evaluate suicidal ideation and behavior among study participants. The C-SSRS measures 5 possible levels of suicidal ideation

and 4 possible suicidal behaviors, as well as nonsuicidal self-injurious behavior. The assessment is a fully-structured, participant self-report C-SSRS questionnaire, including standardized questions, follow-up prompts, error handling routines, and scoring conventions. Two versions of the C-SSRS will be used in this study, the *Baseline/Screening* version and the *Since Last Visit* version. The *Baseline/Screening* version will be conducted during the screening visit and the *Since Last Visit* version will be conducted at all other visits.

At the screening visit, the C-SSRS should be completed as the first assessment after signing informed consent and before any other tests, procedures, or other consultations. For subsequent visits, the C-SSRS should be completed after all PROs and before any other tests, procedures, or other consultations. Participants will be interviewed by the investigator or trained study site personnel in a private, quiet place.

The following are C-SSRS categories and have binary responses (yes/no). A “yes” response to any C-SSRS category will be assigned a score as below:

Suicidal Ideation (1-5)

1 = Wish to be Dead

2 = Nonspecific Active Suicidal Thoughts

3 = Active Suicidal Ideation with Any Methods (Not Plan) without Intent to Act

4 = Active Suicidal Ideation with Some Intent to Act, without Specific Plan

5 = Active Suicidal Ideation with Specific Plan and Intent

Suicidal Behavior (6-10)

6 = Preparatory Acts or Behavior

7 = Aborted Attempt

8 = Interrupted Attempt

9 = Actual Attempt (nonfatal)

10 = Completed Suicide

If no events qualify for a score of 1 to 10, a score of 0 will be assigned (0 = “Negative result [no suicidal ideation or behavior]”). Higher scores indicate greater severity.

Suicidal ideation and behavior will be summarized based on the most severe/maximum post baseline C-SSRS outcome or AE of suicidal ideation, suicidal behavior excluding completed suicide, or completed suicide. In addition, frequency distribution of the most severe/maximum post baseline C-SSRS outcome will be tabulated by C-SSRS categories. The baseline is defined as the most severe/maximum C-SSRS score at either screening or Week 0.

The maximum score assigned for each participant will also be summarized into one of three broad categories: No suicidal ideation or behavior, suicidal ideation, suicidal behavior. A shift table for change in C-SSRS categories of no suicidal ideation or behavior, suicidal ideation, and suicidal behavior from baseline will be presented, where the post baseline is based on C-SSRS or AE data.

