#### **Medical Conditions**

1. The study participant has a total score of JDA severity index for GPP  $\geq 14$  at baseline if participants have a diagnosis of GPP.

2. The study participant has a differential diagnosis of the erythroderma (eg, erythroderma caused by lymphoma or drug eruption) other than EP.
3. The study participant has a history of or current diagnosis or signs or symptoms of severe, progressive, or uncontrolled liver, renal; cardiac, vascular, pulmonary, gastrointestinal, endocrine, neurologic, hematologic, rheumatologic, psychiatric, or metabolic disturbances.
4. The study participant has a history of amyloidosis.
5. Known allergies, hypersensitivity, or intolerance to JNJ-77242113 or its excipients (refer to the IB).
6. The study participant had major surgery, (eg, requiring general anesthesia) within 8 weeks before screening, or will not have fully recovered from surgery, or has surgery planned during the time the participant is expected to participate in the study.

Note: Participants with planned surgical procedures to be conducted under local anesthesia may participate.

7. The study participant had transplanted organ (with exception of a corneal transplant >12 weeks before the first dose administration of study intervention).
8. All participants with:
  - suicidal ideation in the 26 weeks prior to screening that may be defined as a C-SSRS rating of: Wish to be Dead, Non-Specific Active Suicidal Thoughts, or Active Suicidal Ideation with Any Methods (Not Plan) without Intent to Act and is considered to be at risk by the investigator.

Participants  $\geq 18$  years if age with:

- suicidal ideation or suicidal behavior in the 26 weeks prior to screening that may be defined as a C-SSRS rating of: Suicidal Ideation with Intention to Act, Suicidal Ideation with Specific Plan and Intent, Actual suicide attempt, Interrupted suicide attempt, Aborted suicide attempt, or Preparatory behaviors for making a suicide attempt, and is considered to be at risk by the investigator based on an evaluation by a mental health professional.

Participants  $\geq 12$  to  $<18$  years of age with:

- suicidal ideation or non-suicidal self-injurious behavior in the 26 weeks prior to screening that may be defined as a C-SSRS rating of: Suicidal Ideation with Intention to Act, Suicidal Ideation with Specific Plan and Intent, or non-suicidal self-injurious behavior.

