### 8.3.6. Suicidal Ideation and Behavior Risk Monitoring

The C-SSRS defines 5 subtypes of suicidal ideation and 4 possible suicidal behaviors, as well as non-suicidal self-injurious behavior and completed suicide. It will be used as a screening tool to prospectively evaluate suicidal ideation and behavior in this study, as part of a comprehensive evaluation of safety.

Two versions of C-SSRS will be used in this study: the ‘Baseline/Screening’ version of the C-SSRS will be conducted during the screening visit and the ‘Since Last Visit’ version of the C-SSRS will be completed at Week 0 and all other visits through the end of the study. The C-SSRS must be completed after performing PROs and before performing any other tests or study procedures.

The investigator or trained study-site personnel will interview the participant in a private place and complete the C-SSRS. At the conclusion of each assessment, the trained personnel administering the C-SSRS will determine the level of suicidal ideation or behavior, if any. They will then determine the next course of action if any level of suicidal ideation or behavior is reported. The participant should not be released from the site until the C-SSRS has been reviewed by the investigator and the participant’s risk has been assessed and follow-up determined, as appropriate.

For each assessment after Week 0, the following actions should be taken, if applicable:

- a. No suicidal ideation or behaviors (including self-injurious behavior without suicidal intent): No further action is needed.
- b. Suicidal ideation levels 1-3 or non-suicidal self-injurious behavior: Participant risk is assessed by the investigator.
- c. Suicidal ideation levels 4 or 5 or any suicidal behavior: Participant risk assessed and referral to a mental health professional.

Any C-SSRS finding, which in the opinion of the investigator is new or considered to be a worsening and clinically significant, should be reported on the AE eCRF.

In addition, caregivers of the participants will be instructed to immediately report any suicidal ideation, suicidal behavior, or suicide attempt to the investigator.

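### The SAP's C-SSRS outputs have no place for non-suicidal self-injury, so a participant with only that finding looks the same as one with a wholly negative assessment

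*SAP*

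**What the plan says.** SAP 4.5.3.3 describes the scale as covering five levels of ideation "and 4 possible suicidal behaviors, as well as nonsuicidal self-injurious behavior". It then states that a yes "response to any C-SSRS category will be assigned a score as below" and lists ten levels: ideation 1 to 5 and suicidal behavior 6 to 10. NSSIB is not among them. For everyone else, "If no events qualify for a score of 1 to 10, a score of 0 will be assigned", labelled as a negative result with a bracketed gloss that there is no suicidal ideation or behavior.

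The outputs follow from that score. The "frequency distribution of the most severe/maximum post baseline C-SSRS outcome will be tabulated by C-SSRS categories". The maximum score is also grouped into three classes, "No suicidal ideation or behavior, suicidal ideation, suicidal behavior", and a shift table uses the same three. Adverse events enter these outputs only if they are suicidal ideation, suicidal behavior or completed suicide. SAP 4.5.2 plans one listing on the subject, an adverse event listing restricted to suicidal ideation or behavior.

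The protocol refers to NSSIB in two places. Section 8.3.6 sets out actions after Week 0. Item a reads "No suicidal ideation or behaviors (including self-injurious behavior without suicidal intent): No further action is needed"; item b reads "Suicidal ideation levels 1-3 or non-suicidal self-injurious behavior: Participant risk is assessed by the investigator". Exclusion criterion 8, in the part for ages 12 to under 18, covers "suicidal ideation or non-suicidal self-injurious behavior in the 26 weeks prior to screening" and names NSSIB as one of the C-SSRS ratings that define it. On analysis, protocol 9.3.5 says that changes in C-SSRS will be summarized and, under its C-SSRS heading, that suicide-related thoughts and behaviors will be summarized descriptively.

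**The concern.** The SAP names a finding as measured and then plans no output that shows it. The protocol thinks the finding important enough to call for an investigator's risk assessment and, in adolescents, to exclude for recent occurrence. Someone reading the C-SSRS tables could not tell whether a score of 0 meant a clean assessment or one that set off a risk assessment at the visit.

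At stake is the completeness of the psychiatric safety report in a trial that enrols from age 12 and has no data monitoring committee. Each disease group has a target of 8 participants, so a single case is worth being able to see. No efficacy result depends on this.

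**Working it through.** No figure in the plan needs reproducing. The check applies the SAP's scoring rule to defined cases and then searches the SAP for any other place where NSSIB would show.

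**Step 1: the rule applied (SAP 4.5.3.3).**

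| C-SSRS findings | Score | Broad class | NSSIB visible in a C-SSRS table? |
|---|---|---|---|
| None | 0 | No ideation or behavior | Not applicable |
| NSSIB only | 0 (default rule) | No ideation or behavior | No |
| NSSIB and ideation | 1 to 5, from the ideation | Ideation | No |
| NSSIB and suicidal behavior | 6 to 10, from the behavior | Suicidal behavior | No |

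The first two rows are identical in every output. The SAP does not say in so many words that NSSIB scores 0; this follows from the default.

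**Step 2: baseline and shift.** Baseline is the maximum score at screening or Week 0, so NSSIB alone at baseline is also 0. A participant with no ideation or suicidal behavior who self-injures for the first time on treatment moves from 0 to 0 and counts as unchanged. An adult with NSSIB at baseline, whom criterion 8 does not exclude for it, also shows as 0. New and pre-existing NSSIB cannot be separated.

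**Step 3: other SAP outputs.** The listing in SAP 4.5.2 is drawn from adverse events and does not name NSSIB. No listing of C-SSRS responses is planned, although the SAP does list laboratory values, vital signs, relevant ECG abnormalities and PHQ-9 scores for participants at 15 or above. The table of changes to protocol-planned analyses (SAP 4.8) records no decision to leave NSSIB out. Count: 0 C-SSRS table rows and 0 C-SSRS listings show it.

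**Step 4: set against the protocol.** Item a of 8.3.6 is awkwardly worded, and its parenthesis could be misread as putting NSSIB in the no-action group. Item b settles it: NSSIB goes to risk assessment together with ideation levels 1 to 3. The SAP reports ideation 1, 2 and 3 level by level and gives no place to the other finding in the same item.

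**The case against.** The case for leaving the SAP alone is a good one.

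- **The label is true.** Read in full, score 0 says there is no suicidal ideation or behavior, and NSSIB is by definition not suicidal. The tables are silent on NSSIB; they do not assert that it is absent. This stands.
- **The protocol's C-SSRS paragraph in 9.3.5 promises only suicide-related thoughts and behaviors.** It does, and no named analysis has been dropped. But the same section also promises changes in C-SSRS more generally, and criterion 8 treats NSSIB as a C-SSRS rating, so reporting it is within the protocol's scope.
- **Items a to c of 8.3.6 are actions for the site and not reporting classes.** Correct. The SAP's ideation class itself spans items b and c. The items show that the protocol regards NSSIB as a finding; they do not dictate table rows.
- **The event has another route.** New on-treatment self-injury reasonably falls under the general adverse event definition in Appendix 3, which requires all adverse events to be recorded, and SAP 4.5.2 tabulates and lists all treatment-emergent events. With about 16 participants, a reader of that listing could find it. This stands in large part. However, the C-SSRS-specific instruction in 8.3.6 depends on the investigator judging the finding new or worsening and clinically significant, and an NSSIB adverse event still does not feed the C-SSRS tables.

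A reader might go further and infer that the SAP would report a false zero. The documents do not support that. The tabulated variable is suicidal ideation or behavior, and zero is the right count for a participant with NSSIB only. A count of NSSIB would be a different variable, not a correction. Nor is NSSIB an exclusion for everyone: that part of criterion 8 covers ages 12 to under 18 only.

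**Conclusion.** The point holds as a reporting gap of minor severity and is best treated as a free improvement. No planned count is wrong, no named analysis is missing and no endpoint changes. What is missing is any C-SSRS output that shows a finding the SAP itself says the scale measures.

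The statement that an NSSIB participant looks wholly negative applies when NSSIB is the only C-SSRS finding; otherwise it is masked by the higher score. It would be too strong to say that the event is lost from the study report, since the adverse event outputs may carry it. The practical effect depends on whether any participant has NSSIB, which the documents cannot tell us. The conclusion assumes that the NSSIB response is held in the database as part of the C-SSRS, as the instrument's description in protocol 8.3.6 and SAP 4.5.3.3 implies.

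**What to change.** In SAP 4.5.3.3:

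1. Keep the 0 to 10 score and its categories as they are.
2. Relabel score 0 simply as no suicidal ideation or behavior, dropping the words that call it a negative result. This avoids having a zero score that sometimes carries the label and sometimes does not.
3. Add a separate yes/no row for NSSIB, at baseline and at any post-baseline visit, by GPP, EP and GPP+EP.

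In SAP 4.5.2, add participants with any NSSIB to the suicidality listing. That listing is currently drawn from adverse events, so its source needs widening to include the C-SSRS responses.

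The cost is a few lines of SAP text, one table row and one extended listing. Nothing new is collected, and no protocol change is required.
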